2.4.2. Standard Oncology Care

Participants assigned to the control arm will receive standard oncology care provided by their oncologist and will not have any further contact with the study doctor following randomisation. The treating clinicians will be blinded to the results of any study assessments. Assessments of outcome measures occur at 12 weeks, 18 weeks and 24 weeks following randomisation. After 24 weeks, participants will no longer be required to complete further study assessments. Although participants in the control arm may be referred to a geriatrician at any time by their treating clinicians, they will not be permitted to cross-over to receive the study-specific comprehensive geriatric assessment and management.

2.5. Data

2.5.1. Collected Data

Required Forms	Baseline	Week		
		12	18	24 / End of Study
PARTICIPANT FORMS				
Participant Information and Consent Form	X			
Medicare Participant Consent Form (optional)	X			
Global Rating of Change		X	X	X
ELderly Functional Index (ELFI)	X	X	X	X
EORTC QLQ-C30 v3.0 and QLQ-ELD14	X	X		X
EQ-5D-5L	X	X	X	X
Function – ECOG, KPS, ADL, IADL	X	X		X
Mood – PHQ-9 and GAD-7	X	X		X
Nutrition – self-MNA and G8 Screening Tool	X	X		X
Social situation	X	X		X
RESEARCHER FORMS				
Demographics	X			
Medical History (including Charlson Comorbidity Index)	X			
Concurrent medications	X	X		X
TUG	X	intervention group		intervention group
Physician-rated ECOG and KPS	X	intervention group		intervention group
CHSA Clinical Frailty Scale	X	intervention group		intervention group
Flemish Triage Risk Screening Tool (fTRST)	X	intervention group		intervention group
Level of care	X	X		X
Height	X			
Weight	X	X		X
Blood test results (FBE, UEC)	X			
Chemotherapy treatment		X		X
Healthcare utilisation		X		X
CoMiDa Form	X	X	X	X
Overall survival		To cut-off date (to be determined)		

2.6. Endpoints

2.6.1. Summary of Endpoints

The primary and secondary endpoints are summarised in the table below. The primary endpoint of this study is health-related quality of life (HRQOL). The secondary endpoints are survival, function, mood, nutrition, chemotherapy delivery, healthcare utilisation and institutionalisation.

Primary Endpoint	Measures
ELderly Functional Index (ELFI)	
The ELderly Functional Index (ELFI) consists of the linear transformation from 0-100 of the unweighted summed score of 12 items from the QLQ-C30 and QLQ-ELD14, covering: physical functioning (PF2; QLQ-C30 items 1-5), role functioning (RF2; QLQ-C30 items 6-7), social functioning (SF; QLQ-C30 items 26 and 27) and mobility (MO; QLQ-ELD14 items 31, 33 and 34).
 
The individual scales on the QLQ-C30, QLQ-ELD14 and EQ-5D-5L will be reported in the secondary and tertiary HRQOL analyses to assist in interpretation of the primary endpoint.

Secondary Endpoints	Measures
Survival	
 Overall survival
Function	
 Self-reported ECOG performance status Self-reported Karnofsky performance status Katz ADL scale OARS IADL scale
Mood	
 PHQ -9 GAD-7
Nutrition	
 Self-MNA
Health Utilities	
 EQ-5D-5L
Chemotherapy delivery	
 Initial dose (standard or reduced dose) Subsequent dose (dose delay or dose reduction, discontinuation of chemotherapy)
Healthcare utilisation	
 Hospitalisation (number, type, length of hospital stay, reason) Emergency department visits (number, reason) Referrals (type, date referred, date seen) including Allied Health and Oncology Rehabilitation Program Medical consultations Type of Pharmaceutical Benefit Scheme (PBS)-listed medications
Institutionalisation	
 Social situation Level of care

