Components of the CGA (e.g. comorbidity, functional status, geriatric syndrome, nutritional status) have high prognostic value for predicting morbidity and mortality in older adults.(16-20) In addition, two recent large studies developed models for predicting chemotherapy toxicity in older adults with cancer which includes geriatric variables. In the model developed by the Cancer and Aging Research Group, the geriatric variables that predicted chemotherapy toxicity included: age ≥ 72 years, hearing impairment, history of falls, dependence on medication administration, limitation in mobility and decreased social activity.(21) In another model known as the Chemotherapy Risk Assessment Scale for High-Age Patients (CRASH) score, the geriatric variables that predicted chemotherapy toxicity in patients aged ≥ 70 years included: dependence in instrumental activities of daily living (IADL), impaired mini-mental status examination (MMSE) score and impaired mini-nutritional assessment score (MNA).(22) Both chemotherapy toxicity prediction models are currently undergoing external validation.

Geriatric assessment can also influence treatment decisions with two published studies demonstrating that geriatric assessment prior to chemotherapy led to modification in chemotherapy regimen in 39-50% of patients.(23, 24) In one study of 161 patients, pre-chemotherapy geriatric consultation resulted in 76% of patients undergoing some form of geriatric intervention and 49% of patients having modification of the initially proposed chemotherapy regimen – these modifications consisted of higher intensity therapy in 28%, lower intensity therapy in 18% and delayed therapy in 3%.(23)

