3.7. Study endpoints

3.7.1. Summary of Endpoints

The primary and secondary endpoints are summarised in the table below. The primary endpoint of this study is health-related quality of life (HRQoL). The secondary endpoints are survival, function, mood, nutrition, chemotherapy delivery and healthcare and aged care service utilisation.

Primary Endpoint	Measures
Trial Outcome Index	
The Trial Outcome Index (TOI) consists of the linear transformation from 0-100 of the unweighted summed score of the physical functioning (PF2), role functioning (RF2) and social functioning (SF) scales of EORTC QLQ-C30, with the mobility (MO) scale of the QLQ-ELD14.
 $TOI = PF2 [QLQ-C30] + RF2 [QLQ-C30] + SF [QLQ-C30] + MO [QLQ-ELD14]$ 
The individual scales on the QLQ-C30, QLQ-ELD14 and EQ-5D-5L will be reported in the secondary and tertiary HRQoL analyses to assist in interpretation of the primary endpoint.

Secondary Endpoints	Measures
Function	
 • ECOG performance status (self-reported) • Karnofsky performance status (self-reported) • Katz ADL scale • OARS IADL scale

Survival	
 • Overall survival
Mood	
 • PHQ -9 • GAD-7
Nutrition	
 • Self-MNA
Health Utilities	
 • EQ-5D-5L
Chemotherapy delivery	
 • Initial dose (standard or reduced dose; dose adjustments due to CGA) • Subsequent dose (dose delay or dose reduction, discontinuation of chemotherapy due to toxicity)
Healthcare utilisation	
 • Hospitalisation (number, type, length of hospital stay, reason) • Emergency department visits (number, reason) • Referrals (type, date referred, date seen) • Medical consultations • Type of Pharmaceutical Benefit Scheme (PBS)-listed medications
Institutionalisation	
 • Social situation • Level of care

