3.2. Sample size

3.2.1. Sample size required

Based on reviews of published studies, a minimal important difference in patient-reported outcome scores has commonly been set at approximately half the standard deviation; that is, equivalent to an effect size of 0.50.(20, 21) An effect size of 0.5 is commonly regarded as a medium difference and a meta-analysis has shown it to be clinically relevant in studies of quality of life using QLQ-C30 as an outcome measure.(22, 23)

The target sample for this study was based on an independent t-test at a 2-sided significance level of 0.05 to have an 80% power to detect a significant between-group difference in ELFI from baseline to 12 weeks with an effect size of 0.5. Under these assumptions, the minimum sample size is 64 evaluable participants in each group (or a total of approximately 128 evaluable participants) who have completed the primary outcome measure at two separate timepoints.

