- Institutionalisation A secondary endpoint of this study is the hazard ratio of institutionalisation of participants in the two treatment arms; this will be compared between treatment arms. In addition, the level of care level of care and social situation will also be described in the treatment arms.

The following endpoint definition was changed from the protocol:

- Chemotherapy delivery: the proportion of participants with dose delays in the two treatment arms at 12 weeks and 24 weeks. Dose delay is defined as a delay of more than 3 days in the start of chemotherapy measured since the start of the previous cycle.

The following endpoints were not defined in the protocol, but will be analysed as exploratory endpoints to supplement the pre-specified secondary endpoints:

- QLU-C10D health utility
- QLU-C10D health utility score in the two treatment arms at 12 weeks and 24 weeks will be compared between treatment arms.(27, 28)
- The QLU-C10D health utility scores will also be used in the health economic analysis, in place of the EQ-5D-5L scores, to determine if the same or different conclusions would be reached with either utility measure.
- Chemotherapy delivery
- Primary dose reduction (PDR) will be compared within treatment arms. PDR is defined as dose of chemotherapy which is less than the dose recommended for given regimen in current treatment guidelines by NCCN (excluding round-off).
- Mean % dose reduction at outset will be compared within treatment arms.
- Median % dose reduction at outset will be compared within treatment arms.
- Early discontinuation of chemotherapy will be compared within treatment arms.
- Mean cycles of chemotherapy delivered will be compared within treatment arms.
- Median cycles of chemotherapy delivered will be compared within treatment arms.

Table 4. Summary of secondary and additional exploratory endpoints, data type, data timepoints and statistical tests are listed in the table below.

Endpoints	Data Type	Data output	Data Timepoints	Statistical Tests
Function				
ECOG-PS	Categorical ordinal (0,1,2,3,4)	contingency table	Baseline Wk12 Wk24	contingency table analysis
KPS	Categorical ordinal (30,40,50,60,70,80,90,100)	contingency table	Baseline Wk12 Wk24	contingency table analysis
Katz ADL scale	6-item, categorical dichotomous scale (i) → dichotomous outcome (unimpaired, impaired) (ii) → dichotomous outcome (any decrease in ADL)	1. unimpaired vs impaired 2. decrease in ADL	Baseline Wk12 Wk24	contingency table analysis

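### The SAP drops the reason qualifiers from two chemotherapy-delivery measures without declaring it, so discontinuation due to toxicity becomes any-cause and exploratory

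*Combined protocol and SAP*

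**What the plan says.** The endpoint table in protocol 3.7.1 gives two lines for chemotherapy delivery, both secondary: "Initial dose (standard or reduced dose; dose adjustments due to CGA" and "Subsequent dose (dose delay or dose reduction, discontinuation of chemotherapy due to toxicity". Each carries a reason.

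The corresponding table in SAP 2.6.1 still lists chemotherapy delivery as secondary. The initial-dose line now says only standard or reduced, and the second line reads "Subsequent dose (dose delay or dose reduction, discontinuation of chemotherapy". Both reasons are gone. Table 4 follows suit: initial dose (full or reduced) and early discontinuation (yes or no) are analysed by contingency table with no reason.

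SAP 3.5.2 has a short list of definitions that differ from the protocol. Dose delay is its only entry. A further list, of exploratory endpoints said to be absent from the protocol's definitions, includes primary dose reduction and early discontinuation: "Early discontinuation of chemotherapy will be compared within treatment arms".

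**The concern.** A secondary measure that the protocol tied to toxicity has become an any-cause measure, has been moved to exploratory in one section of the SAP while staying secondary in another, and is described as new. A reader who relies on the SAP's own list of changes would not find this out.

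The reason also carries the meaning. SAP 1.3 hypothesises that integrated care improves chemotherapy delivery. Protocol 1.2.1 names dose modification as one possible consequence of a geriatric assessment, and under SAP 2.4.1 and 2.4.2 the study assessment reaches the treating oncologist in the intervention arm only. Stopping for toxicity is a failure of tolerance. Stopping for progression, death, patient choice or on assessment advice is something else. Counted together, more stopping in the intervention arm could mean worse tolerance or deliberate tailoring, and less toxicity could be offset by other reasons.

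**Working it through.** **1. The texts side by side**

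| Item | Protocol 3.7.1 | Protocol 3.7.3.7 | SAP 2.6.1 | SAP 3.5.2 and Table 4 |
|---|---|---|---|---|
| Initial dose | secondary; adjustments from the assessment identified | not mentioned | secondary; no reason | primary dose reduction, exploratory, called new; no reason |
| Discontinuation | secondary; toxicity | not mentioned | secondary; no reason | exploratory, called new; no reason |
| Reduction of at least 10% | no threshold; toxicity wording most naturally belongs to discontinuation | no cause | no cause | secondary; no cause |
| Delay | as above | over 14 days, no cause | no cause | over 3 days, no cause; change declared |
| Relative dose intensity | not listed | no cause | not listed | secondary; no cause |

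The protocol synopsis lists dose, adjustments, delays and discontinuation with no cause. The undeclared loss therefore affects the first two rows only.

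**2. The plan's own sample size**

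SAP 3.2.1 uses "an independent t-test at a 2-sided significance level of 0.05 to have an 80% power" and a "between-group difference in ELFI from baseline to 12 weeks with an effect size of 0.5", and concludes that "the minimum sample size is 64 evaluable participants in each group". The normal approximation gives n = 2(1.96 + 0.8416)²/0.5² = 62.8, so 63 per arm. The exact t-test gives 63.77, so 64, with power 0.801. The figure reproduces. It concerns the primary endpoint; no chemotherapy measure is powered.

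**3. What any-cause counting does to discontinuation**

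Let the toxicity-stopping proportions be p_c (control) and p_i (intervention).

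- If a share s of the remaining patients in each arm stops for other reasons, the any-cause gap is [p_c + (1 − p_c)s] − [p_i + (1 − p_i)s] = (p_c − p_i)(1 − s). The gap shrinks even when the other reasons are balanced.
- If a share c of the remaining patients stops on assessment advice in the intervention arm only, that arm's rate is p_i + (1 − p_i)c.

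The documents give none of these rates, so all values below are assumptions. Take 64 per arm, two-sided 0.05, and power = Φ{[|d| − 1.96√(2p̄(1 − p̄)/n)] / √([p_c(1 − p_c) + p(1 − p)]/n)}, where p is the intervention arm's rate, d = p_c − p and p̄ is the average of p_c and p.

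Worked case: p_c = 0.30, p_i = 0.15, c = 0.10. The intervention rate is 0.15 + 0.85 × 0.10 = 0.235, so d = 0.065 and p̄ = 0.2675. The two standard errors are 0.0783 and 0.0780. The argument is (0.065 − 1.96 × 0.0783)/0.0780 = −1.13, and power is 0.13.

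| Toxicity stopping, control vs intervention | Toxicity only | c = 3% | c = 5% | c = 10% | c = 18% |
|---|---|---|---|---|---|
| 30% vs 15% | 0.53 | 0.38 | 0.29 | 0.13 | 0.03 |
| 40% vs 20% | 0.70 | 0.58 | 0.49 | 0.30 | 0.10 |
| 30% vs 10% | 0.82 | 0.67 | 0.56 | 0.30 | 0.07 |

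In the first row the intervention arm's any-cause rates are 17.6%, 19.3%, 23.5% and 30.3% against 30%, so at c = 18% the gap has closed. The table shows that masking is possible. It does not estimate how much would occur.

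**The case against.** A reader might infer that the whole family of chemotherapy endpoints has been stripped of causes, and that assessment-led dose reductions will cancel a toxicity benefit. The documents do not support that, for four reasons.

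- **Most of these endpoints never had a cause.** Protocol 3.7.3.7 defines relative dose intensity, reduction of at least 10% and delay without one, and the SAP removed nothing there.
- **Initial and later reductions are not pooled.** Table 4 gives initial dose its own row, and later reduction is measured against the previous dose. One could combine 18% advised reductions with 15% toxicity reductions, 1 − 0.82 × 0.85 = 30.3%, and set that against 30% in control. No such endpoint exists. If the advised changes are all made at the outset, the later-reduction row still reads 15% against 30%.
- **The direction is open.** The cited pre-chemotherapy study found "higher intensity therapy in 28%, lower intensity therapy in 18% and delayed therapy in 3"%. If every changed dose moved by an assumed 20% to 30%, the reductions alone would lower mean relative dose intensity by 18% × 20% to 18% × 30%, or 3.6 to 5.4 points. With the increases included, the net is (28% − 18%) × 20% to 30%, a rise of 2.0 to 3.0 points.
- **Any-cause counts have a merit.** In an open-label trial, attributing a stop to toxicity or to advice is a judgement, and the any-cause count avoids it.

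It can also be said that protocol 3.7.3.7 gives no operational definition of discontinuation, so calling it undefined is literally arguable. But protocol 3.7.1 lists it as secondary and names the reason, so presenting it as a new exploratory endpoint is wrong.

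The first three objections stand against the wider reading, and the fourth is a reason to keep the any-cause result. None removes the undeclared change to discontinuation and initial dose. Nor does the separate initial-dose row settle everything. The assessment may come up to 3 weeks after randomisation, its written report up to 2 weeks later, and reviews follow at about 12 and 24 weeks, while protocol 3.6.5.3 expects some patients to start chemotherapy before day 8. Some advised changes can therefore fall after the first cycle.

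**Conclusion.** The point holds for two measures. The reasons attached in the protocol to initial-dose adjustments and to discontinuation are missing from the SAP, the change is not declared, and SAP 3.5.2 is wrong to treat primary dose reduction and early discontinuation as new. The SAP also disagrees with itself on whether they are secondary (2.6.1) or exploratory (3.5.2).

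As written, any-cause discontinuation cannot be read as a measure of tolerance, and a benefit could be masked. The power figures rest wholly on assumed rates and on 64 analysed per arm. The 18% in the cited study is a share given lower-intensity treatment, not a stopping rate. Neither the size nor the direction of any distortion can be taken from the documents.

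The measures are secondary or exploratory and unpowered, and the primary ELFI analysis is untouched. This should be corrected before analysis, but it does not threaten the main result.

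**What to change.** 1. In SAP 3.5.2, declare both deletions and correct the statement that early discontinuation and primary dose reduction were not in the protocol.
2. Reconcile the protocol synopsis, protocol 3.7.1 and 3.7.3.7, SAP 2.6.1 and 3.5.2, and Table 4, so that each measure has one definition and one status.
3. Restore discontinuation due to toxicity as the protocol-listed secondary measure, compared between arms. SAP 3.5.2 currently speaks of comparison within arms. Report any-cause discontinuation beside it, and tabulate progression, death, choice and assessment recommendation by arm.
4. Flag initial-dose adjustments arising from the assessment descriptively, using the data on recommendations and adherence already planned in protocol 4.5.2.
5. Leave relative dose intensity, reduction of at least 10% and delay as all-reason measures, with reasons described where recorded.

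The cost is SAP wording and a reason code. The forms tables (protocol 3.6.1, SAP 2.5.1) show one line for chemotherapy treatment and no visible reason field, and the SAP describes recruitment in the past tense, so some reasons may have to be coded retrospectively. Attribution would be open-label; one fixed list applied identically in both arms, with the any-cause result kept, limits that weakness.

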2.7. Study endpoints

2.7.1. Primary Endpoint

The primary objective of this study was to assess the effects of integrated geriatric care on HRQOL in older adults (>70 years) with cancer receiving chemotherapy. The EORTC QLQ-C30 version 3.0, QLQ-ELD14 and EQ-5D-5L will be used to measure HRQOL.

The primary endpoint of this study was the ELderly Functional Index (ELFI). Previous versions of the study protocol designated the ELFI as the Trial Outcome Index, but the endpoint definition remains unchanged (i.e. ELFI = Trial Outcome Index).

ELFI consists of the linear transformation from 0 to 100 of the unweighted summed score of 12 items from the QLQ-C30 and QLQ-ELD14, covering: physical functioning (PF2; QLQ-C30 items 1-5), role functioning (RF2; QLQ-C30 items 6-7), social functioning (SF; QLQ-C30 items 26 and 27) and mobility (MO; QLQ-ELD14 items 31, 33 and 34). A higher score on the ELFI represents higher (“better”) functioning. The individual scales on the QLQ-C30, QLQ-ELD14 and EQ-5D-5L will be reported in the tertiary HRQOL analyses to assist in interpretation of the primary endpoint and to provide a comprehensive assessment of the impact of the intervention on all domains of HRQOL assessed. Note that most of these scales contain multiple items (multi-item scales), whilst the remainder contain only one item (but are still called scales). Following convention, we will not report or analyse separately any items that are aggregated into multi-item scales.

2.7.2. Secondary Endpoints

2.7.2.1. Overall Survival

Overall survival is defined as the time from randomisation until death due to any cause. Participants who are alive (including lost to follow-up) at the time of the analysis will be censored at the date when they were last known to be alive.

2.7.2.2. Performance status

Performance status is used to assess functional performance in cancer patients and is part of routine oncology care. Performance status is a powerful predictor of HRQOL and survival and is an important concern in cancer patients. ECOG and KPS are both widely used methods of assessing performance status of cancer patients. Self-rated ECOG and KPS score will be used to describe the performance status of the study population.

The ECOG score is a single item rating of the degree to which the patient is able to participate in typical activities without a need for rest. The scale ranges from 0 (fully active) to 5 (dead) (6) The KPS score is a single item rating of three dimensions of functional status: activity, work and self-care.(7) The KPS is an 11-point rating scale that ranges from 0 (dead) to 100 (normal functioning).

2.7.2.3. Activities of Daily Living (ADL) and Instrumental Activities of Daily Living (IADL)

In geriatric medicine, ADL and IADL is used to assess functional status and is part of routine geriatric assessment.(8) Decline in functional status is associated with adverse health outcomes such as mortality and residential care placement for older hospitalised patients. Self-reported Katz ADL scale and OARS IADL scale will be used to describe the functioning level in of the study population.(9, 10)

Katz ADL scale assesses adequacy of performance in basic activities of daily living: bathing, dressing, toileting, transferring, continence, and feeding. Each item are scored yes/no for independence in each of the six functions. A summary score ranges from 0 (unable to perform any activity) to 6 (able to perform all activities).

OARS IADL is an easy to administer assessment instrument that provides self-reported information about functional skills necessary for independent living in the community. These skills are considered more complex than the basic activities of daily living as measured by the Katz ADL scale. The 7-items on the OARS IADL assesses the following domains of function: telephone, shopping, food preparation, housekeeping, mode of transportation, medications and finances. Each item is scored on a 3-point Likert-like scale, with the total score ranging from 0 (unable to perform any activity) to 14 (able to perform all activities).

Disability in ADL and IADL is defined as the need for assistance to complete at least one ADL or IADL, respectively. Functional decline in ADL and IADL is defined as any decrease in ADL and/or IADL score between baseline and follow-up assessments.

